#### ***Adequacy of protection against risks***

##### **Recruitment and informed consent procedures**

First, the Duke Institutional Review Board (IRB) will review and approve the study protocol before study initiation (as they did for our preliminary work conducted under Duke IRB Protocols #00062340, #00069031, and #00071161). Informed consent (verbal, e-consent, or written) will be required from all participants. Second, we will use a standardized screening and enrollment protocol that respects participant privacy and rights. Clinical research coordinators will approach patients to discuss the study at the time the BLUE CORAL participant is on the phone completing a BLUE CORAL survey. This will be possibly be aided by a short IRB-approved recruitment video we have produced and piloted for LIFT, similar to other highly rated videos our group has made for similar purposes in other clinical trials. After following the verbal consent script, the clinical research coordinator will then obtain verbal informed consent from the participant. If a patient wishes to do e-consent, this procedure will be followed as described above in Section 6.B. Potential subjects will have up to 72 hours to consider enrollment. For the clinical trial, we will take great care to present the treatment group

assignment possibilities ("like drawing a number out of a hat") tactfully and with clearly stated equipoise in person, as we have done successfully in past ICU-based clinical trials. A copy of the consent form will be emailed or mailed to participant (as they prefer) and the original maintained in the study data system (e-consent) or in a secure location at the study site (mailed consent). The study team will provide contact information for the PI.

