(5) As a safety measure that we have used in past/current clinical research, the study team will be trained to monitor participants closely beyond just the parameters of questionnaire scores. The study staff, including the trained clinical research coordinators and the therapist, will monitor participants closely during any interviews performed and will refer those with any concerning level of emotional distress and/or relationship distress to the PI to evaluate by phone. This will be done immediately, particularly if there is staff concern about a participant who indicates suicidality. Point #6 below describes PI actions that will follow.

(6) We have developed a specific protocol to manage any study participant who expresses suicidal thoughts in person, by telephone, or via the app at any point during the study. All study participants will be informed of this suicidality response plan prior to signing the informed consent for their participation in the study. The PI or trained CRC will complete the online Columbia Suicide Severity Rating Scale (C-SSRS) training, a 30-minute interactive slide presentation followed by a question-answer session. The C-SSRS is scale that can delineate high, moderate, and low-risk levels.

Our Suicidality Response Plan can be activated in two main ways.

First, study staff (coordinators, therapists, investigators, PI) may have in-person or telephone interactions that concern them.

Second, the study app system will automatically detect any endorsement of active suicidal intent in a 2-step process that is contingent on the PHQ-9's item #9 (which evaluates suicidal thoughts) and the C-SSRS item #4 (which evaluates intent by asking: *Have you had these thoughts and had some intention of acting on them?*) as shown here:

PHQ-9 item 9 response	Suicidal intent item response	Action by app system	Action by team
0	n/a	n/a	n/a
1, 2, or 3 (i.e., ≠ 0)	NO	n/a	n/a
1, 2, or 3 (i.e., ≠ 0)	YES	Alert to study manager, therapist, and PI	Immediately contact participant

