If the participant is deemed to be at high risk for active suicidality based on direct interaction or the PHQ-9 item plus the C-SSRS item response, the app system will send an alert email and/or text message in real time to the study manager, the study therapist, and relevant site PI (no PHI included, only study ID). One of these study staff will then immediately contact the participant. Using the full C-SSRS, the trained staff will then help to assess the participant to determine if they endorse active suicidal ideation. The trained staff will also determine if the participant is currently being treated by a mental health professional.

If the participant is considered to be actively suicidal then at least one of the following plans will be followed depending on the location of the participant for each of the following situations:

Situation 1. If the participant is with one of the study personnel [not expected to occur in the RCT]:

a. The study personnel will notify the PI immediately

b. The study personnel will either physically walk the subject to the emergency department, or call a Psychiatric Emergency services number relevant to the site as described above.

Situation 2. If the participant is on the telephone:

a. The study personnel will notify the PI immediately.

b. The study personnel will stay on the telephone with the subject participant.

c. The study personnel will immediately contact 911 to initiate an on-site rescue if such action is clinically indicated.

d. The study personnel will stay on the telephone with the subject until EMS services have contacted the participant.

Situation 3. If there are any active suicidal concerns in any of the surveys (e.g., PHQ-9 above):

- a. The study data system will notify the PI and Study Manager immediately.
- b. The study personnel will then contact the honest broker to de-identify the participant information.
- c. Next, the study personnel will contact the participant by telephone.
- d. The study personnel will stay on the telephone with the subject participant.
- e. The study personnel will use a different telephone line to immediately contact 911 to initiate an on-site rescue if action is clinically indicated.
- f. The study personnel will stay on the telephone with the subject until EMS services have contacted the participant.

If the participant is determined to be actively suicidal and require immediate medical therapy, they will be withdrawn from the study.

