(8) Finally, though there were no patient deaths during the LIFT COVID RCT follow-up period, we recognize that we are working with a seriously ill population that is at risk for death during follow up due to their underlying illness. We are very sensitive to issues surrounding patient death in relation to study procedures and interviews. We have dealt with this respectfully for years in our studies involving in-person, telephone, and app-based interviews and surveys. On phoning any participant, we will initiate a conversation in a sensitively scripted manner to tactfully ascertain the patient’s vital status should a family member answer first. If the patient has died, we will provide brief support. If a patient states that they wish to drop out, we will respect that as well.

Vulnerable populations. We will not enroll patients from vulnerable populations (e.g., imprisoned persons, minors).

Adverse events (AEs), serious adverse events, (SAEs) and unanticipated problems (UPs). Our plan for AEs, SAEs, and UPs has been reviewed and accepted by the NIH. As mentioned before, we recognize that there is a slight risk that some participants may become distressed when completing self-report measures or participating in interviews. In our previous studies using similar self-report surveys (telephone, in person, or ePRO), we have encountered little resultant distress. In fact, many participants have reported that they were relieved to be able to have a platform through which to reflect on such issues. When necessary, participants who experience psychological distress related to completing questionnaires will be referred for appropriate

Pro00106306: Addressing psychological distress symptoms among serious illness survivors of a viral pandemic with a completely self-directed, symptom-responsive mobile mindfulness intervention

psychiatric or psychological care. All participants will have access to a PI's mobile phone number available 24 hours a day (shown in the consent form). If a telephone interview is required, it will be conducted by an experienced interviewer who has been trained to be sensitive to the nature of these issues.

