In this trial, we expect AEs to be extremely uncommon because it is a behavioral trial. However, it is possible that participants could become distressed in an ICU setting in the event that their loved one dies or becomes more ill. One particular symptom of note that will be considered an AE and reported to the IMC will be suicidal ideation as operationalized by responding to PHQ-9 item #9 (Thoughts that you would be better off dead or of hurting yourself in some way) with either 'more than half the days' or 'nearly every day' out of the preceding 2 weeks. In this trial, we do not anticipate any SAEs because it is a behavioral trial. A SAE in this trial would include a suicide attempt, a hospitalization, or death. All serious adverse events will be reported within the standard timelines required to these bodies as well as to the OHRP and the NIH/NCCIH. AEs and SAEs will be reported to these agencies per their standard guidelines.

While we do not anticipate any UPs because it is a behavioral trial that focuses on ICU patients, critical illness and its recovery process are unpredictable. Unanticipated problems will be identified, discussed by the PIs, and resolved by group consensus. Therefore, should there be unanticipated problems observed we propose the following reporting process—itself framed by NIH guidelines. First, the PIs and Duke University will include a written report that will be submitted to the NCCIH, the study DSMB, and the Central IRB that will describe the UP, the context, and the proposed corrective plan. This written report will be provided within 1 week (unless it/they is/are also an SAE, in which case the timeline for SAE reporting will be followed). The UP will also be forwarded OHRP using [[contact]](mailto:[contact]) within two weeks of the event.

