### Reporting Procedures

We have a strong plan for AE reporting and follow up. First, we have a very robust monitoring system for psychiatric and emotional symptoms. For all groups, we will know 'alert' values of depression, anxiety, and PTSD symptoms the second a questionnaire is completed. For the mobile mindfulness study arm, we will also know depression / anxiety symptoms weekly as well. For symptoms that are either great in total burden (i.e., total score is high), we will call the participant to check in. For specific symptoms such as the suicidal ideation item in the PHQ-9 depression questionnaire, we will also call the participant and assess the severity of the situation, triaging them as appropriate to psychiatric support. For other matters, the study interventionist will also have frequent telephone contact with most participants, and can also refer those with concerning symptoms. Last, we have broadly placed our email addresses and phone numbers in all study materials and will encourage people to contact us regarding any issues.

Since this is a psychosocial intervention, we do not expect study related physical issues to occur. Furthermore, there is no labwork involved.

All deaths will be reported to NIH Program Officer and to the DSMB Chair within 72 hours of study's knowledge of death. For each patient who dies, a brief report containing the following variables will be provided:

Age  
Principal diagnosis  
Number of comorbidities  
Admission APACHE II score  
Days since enrollment  
Brief description of circumstances surrounding death including expected or unexpected.

Serious (fatal or life-threatening) SAEs that are unanticipated (i.e., not listed in the Data and Safety Monitoring Plan) and that are related to the intervention will be reported to the NIH Program Officer and to the DSMB Chair within 7 days of study staff's knowledge of the SAE. The summary of all other SAEs will be reported to NIH Program Officer and to the DSMB quarterly, unless otherwise requested by the DSMB. Additionally, for SAEs, we will hold an all-investigator teleconference within 7 days. The PIs will draft a description of the SAE and an action plan. This will be passed on to the IRB, the NIH, and DSMB within 72 hours of the teleconference.

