Privacy. We will closely safeguard participant privacy regarding protected health and personal information. Study ID numbers, generated randomly at the time of enrollment, are linked in a separate app subsystem that contains patient names and medical record numbers. Further, names, birthdates, telephone numbers, addresses, and medical record numbers will be stored securely as described in the RDSP and only accessible by trained staff listed on the delegation log. The PIs will be unable to view data in the database because they will lack passwords to do so. Data will be delivered to the Duke site from the University of Michigan and PETAL REDCap databases in a scheduled manner and with data use agreements in place with both the University of Michigan and the Massachusetts General Hospital (i.e., PETAL DCC; [Figure 2](#)). Data will be transferred via a Duke Box password protected folder system. These data will be delivered as CSV files for subsequent upload by the statistical team as analytical files (e.g., SAS). No PHI is visible in any user interface, with the exception of the initial survey in which the participant will enter this identifying information. Study participants cannot view data via the app system, only enter data (a 'one-way view'). Patients access this one-way view app system via secure, PHI-free email or text links sent from our study RedCAP data system.

Language specifying the way we use and release data will be shown in the informed consent form as required by the IRB.

Digital security. The study digital infrastructure consists of a mobile (i.e., native) app and a separate RedCAP digital study database. We take digital security very seriously and will follow institutional guidelines for safeguarding data, health information, and study results.

All technology will be managed by the PIs in a collaborative manner.

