### **18.b. LIFT COVID RCT**

As noted above, data use agreements will be put in place to clarify data transferred from both the University of Michigan and the Massachusetts General Hospital and Duke University. Non-BLUE CORAL data will be entered into a LIFT COVID database. Data will be transmitted to Duke in CSV format from PETAL via secure, Duke University-approved, password protected, cloud systems (i.e., Box). These data will be uploaded to a secure, password protected REDCap database housed on a Duke server.

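### The suicidality rule withdraws participants from the study without separating stopping LIFT from ending trial follow-up, so later PHQ-9 values and late non-fatal SAEs may be missed in a few people

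*Combined protocol and SAP*

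**What the plan says.** The rule is the closing sentence of the emergency procedures in Section 15 (oversight plans for severe psychological distress): "If the participant is determined to be actively suicidal and require immediate medical therapy, they will be withdrawn from the study". It covers a narrow group, because both conditions must hold. No visible text defines withdrawal.

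Other parts of the combined protocol and SAP bear on what it means:

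- **Scope of the study.** Section 11 counts both the intervention and the follow-up surveys as part of the five-month study.
- **Triggers.** The plan starts from PHQ-9 item 9 plus an intent item in the app, or because "study staff (coordinators, therapists, investigators, PI) may have in-person or telephone interactions that concern them". Section 7.b gives the weekly in-app PHQ-9 to the LIFT arm only, for four weeks. Section 4.b excludes people with suicidal ideation at the one-month interview.
- **Event recording.** Under Period and Frequency for Event Assessment and Follow-Up, new non-serious AEs are recorded until 7 days, and SAEs until 30 days, after the last day of participation. Recorded events are followed until they resolve or stabilise. On SAEs, Section 15 says: "A SAE in this trial would include a suicide attempt, a hospitalization, or death".
- **Analysis.** Section 10 analyses everyone in the assigned group, whatever their adherence or crossover.
- **Data flow.** The outcome interviews run on the BLUE CORAL timetable (Section 3). On transfer, the Privacy paragraph of Section 15 says: "Data will be delivered to the Duke site from the University of Michigan and PETAL REDCap databases in a scheduled manner".
- **Monitoring.** Section 17 names AE reports and PHQ-9 scores as the DSMB's primary safety measures.

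**The concern.** The event that triggers withdrawal lies in the same domain as the primary outcome. Read with Section 11, leaving the study would end the surveys as well as the app. Staff could reasonably apply the sentence in two ways: stop LIFT and keep calling, or stop everything.

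Under the second reading two things may be missed. One is the T2 and T3 PHQ-9 of people who have just had the most serious event in the outcome domain. The other is a new suicide attempt or hospitalization that starts after the SAE window has closed. Analysis by assigned group does not prevent this, because it settles which arm a value belongs to and not whether the value is collected. For a rare harm, each case matters to the DSMB.

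**Working it through.** **1. The plan's own power.** Inputs from Section 10: difference 2.5, SD 6.0, two-sided 5%, 180 evaluable (90 per arm). If the stated 0.5 is a within-person correlation (assumption), the SD of change is 6 × √(2 × (1 − 0.5)) = 6.0.
- SE = 6 × √(1/90 + 1/90) = 0.894. Power = Φ(2.5/0.894 − 1.96) = 79.8%, against 80% stated. The figure reproduces.
- One LIFT participant lost (89 against 90): SE = 0.897, power 79.6%. Two lost (88 against 90): 79.4%.

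**2. How many people.** Item (7) of the oversight plans reports no acute psychiatric referrals in over 400 participants of past trials, which enrolled family members. Taking 0 of 400:
- One-sided 95% upper bound = 1 − 0.05^(1/400) = 0.00746.
- 0.00746 × 300 = 2.24 people; 0.00746 × 150 = 1.12 per arm.

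**3. Bias at T2 if they are missing.** Bias = p × e/(1 − p), where p is the fraction of LIFT participants missing and e is how far above the arm mean they would score. The value of e is an assumption, 5 to 15 points. All exits are taken to be in LIFT before T2, with no loss in control.
- 1.12 of 150 (p = 0.00746): 0.04 (e = 5), 0.08 (e = 10), 0.11 (e = 15).
- All 2.24 in LIFT (p = 2.24/150 = 0.0149): 0.08 (e = 5) to 0.23 (e = 15).
- If one loss instead comes wholly out of the 90 evaluable: about e/90, or 0.06 to 0.17.

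**4. Lost SAE recording.** With T2 at day 61 and T3 at day 152 after randomization, the planned window per person is 152 + 30 = 182 days. If the exit day d is the last day of participation (assumption), recording ends at d + 30 and the loss is 152 − d.
- Exit at day 7 loses 145 days; day 28, 124; T2, 91; T3, 0.
- Across the trial: 2.24 × 145 = 325 of 300 × 182 = 54,600 person-days, or 0.6%. Exit on day 0 would give 2.24 × 152 = 340, still 0.6%.
- Exits on days 7 to 28 have SAE windows that close on days 37 to 58, before T2. AEs and SAEs are asked about at study visits, so no scheduled interview falls inside those windows.

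**5. What an exit can cost.** Before T2, the T2 and T3 values; at T2, only T3, because the primary endpoint is already in hand; at T3, neither.

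**The case against.** The strongest reply is that nothing need be lost. The T1, T2 and T3 interviews are BLUE CORAL procedures with their own consent, and Table 1 marks only the in-app PHQ-9 as collected for the RCT alone. BLUE CORAL has no visible rule that withdraws people for suicidality. If those calls continue, the data reach Duke on schedule (Section 18.b: "Data will be transmitted to Duke in CSV format from PETAL via secure"), and rehospitalization is asked at T2 and T3. The event that triggered the exit is followed up and logged for the DSMB, deaths are reported within 72 hours of the study's knowledge, and site PIs must report SAEs. The consent form is not visible and may settle the matter. Removing someone in a psychiatric emergency from research can also be a deliberate protection.

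Most of this stands, and it makes the loss conditional. It does not close the gap, because no visible text says the trial may use values collected after withdrawal, or records a new non-fatal SAE that starts after the 30 days.

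Three stronger readings are tempting, and the documents do not support them:

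- **That the rule biases the primary comparison or costs real power.** A reader might take the PI-call rate of under 5% as the exit rate: 15 of 300. With all 15 lost from the 90 evaluable in LIFT, power would be 76.0%. But a PI call is not this trigger, and none of those calls led to acute referral.
- **That exits must fall mainly in LIFT.** Scheduled detection between T1 and T2 is in LIFT only, but telephone contact can start the plan in either arm, and Reporting Procedures says "the study interventionist will also have frequent telephone contact with most participants". An imbalance is possible but not shown.
- **That 50% to 80% of safety follow-up is lost.** For exits between day 7 and T2 (145/182 to 91/182), that is a share of one person's window and rests on an undefined last day.

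**Conclusion.** The point holds as a matter of complete harm and outcome data. The sentence leaves open whether follow-up ends, and the protocol's description of the study makes the wider reading plausible. What is at risk is the later PHQ-9 for trial use, and new non-fatal SAEs that start more than 30 days after exit, in both cases only if BLUE CORAL does not supply them.

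The effect on the trial's primary conclusion is negligible at the rate considered. The main uncertainty is that rate: it comes from family members, not from COVID-19 survivors with a PHQ-9 of 5 or more, so 0 to 2 is not a firm bound, although baseline ideation is excluded. The bias figures rest on the assumed 5 to 15 point excess, and the person-day figure on treating the exit day as the last day of participation. Priority: optional.

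**What to change.** Leave the emergency response unchanged. Replace its final sentence with wording that fits both arms:

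*LIFT use (if assigned) will stop. In both arms, if the participant is willing and clinically able, the T2 and T3 interviews and AE/SAE recording continue as planned, and these values are analysed by assigned arm.*

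A participant's own wish to leave still governs, as Section 15 already provides: "If a patient states that they wish to drop out, we will respect that as well". Report the number, timing and arm of these exits to the DSMB, which already reviews dropout at each meeting, and in the results. If the consent form or script already covers this, bring the sentence into line with it.

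Cost: up to two declinable calls per affected person, on a timetable that BLUE CORAL already runs, plus minor IRB wording and consent wording if needed. Survey payments at 20 dollars each come to at most 2 × 20 = 40 dollars per person, or 80 dollars for two people, within the 60 dollars per participant already planned in Section 14.

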## 8. Randomization.

Figure 1 shows the general approach to screening, informed consent, and randomization. PETAL sites will obtain informed consent for the BLUE CORAL observational study. At the time of the 1-month post-discharge follow up call from the University of Michigan, potential participants will be first screened on the for sufficient distress (i.e., PHQ-9  $\geq 5$ ). For those who meet the cutoff, the staff will describe the LIFT trial and obtain informed consent by phone. For those who provide informed consent, the delegated study staff will enter the data required for randomization (contact information, stratification variable data) into the Shibboleth password-protected Lift app platform study staff dashboard. This will enable auto-randomization by the LIFT platform. Randomization will be stratified by age, gender, and baseline PHQ-9 score.

At this point, an automated SMS text message and/or email (per user preference) will be sent to the participant that alert them to their treatment group. For intervention group participants, it will also provide a link to download the LIFT app platform and a unique ID code to activate it. After download

Figure 1. Screening, consent, and randomization for the LIFT COVID RCT

**Step 1: screening by PETAL / FUNCTION.** The PHQ-9 will be administered by the University of Michigan FUNCTION staff by phone 1 month post-discharge for BLUE CORAL observational study. This will be the baseline (T1) data collection for LIFT.

**Step 2a: consent from PETAL / FUNCTION.** If PHQ-9 eligibility cutoff met, University of Michigan FUNCTION staff obtains informed consent during the phone call.

**Step 2b: consent from Duke center if needed.** If potential participant wishes to think about it, contact data passed to the LIFT sites for either follow up phone call or email-/text-based approach. If participant agrees, LIFT team then sends email and/or text. Participant clicks link in email / text to download the mobile app platform.

**Step 3: randomization.** University of Michigan or LIFT teams add contact data and key variables required for stratification for consented participant to Lift mobile app platform dashboard. The LIFT platform then automatically randomizes the participant into one of the two LIFT COVID groups (LIFT app vs. traditional care control).

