**Step 4: intervention.** Intervention participants receive Lift app access. After T3 (6 month post-discharge) BLUE CORAL survey, traditional care control participants can access Lift if they wish via an email automatically sent from the LIFT platform.

Pro00106306: Addressing psychological distress symptoms among serious illness survivors of a viral pandemic with a completely self-directed, symptom-responsive mobile mindfulness intervention

and activation with the unique ID, the participant's experience will be automated.

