## **9. LIFT COVID RCT procedures**

### ***Aims 1 and 2.***

LIFT is a self-directed mobile app platform based on a solid conceptual model that guides participants through a 1-month program. LIFT content includes 4 weekly app-based sessions as previously tested in a pilot RCT (NCT02701361). Each session is composed of three parts: 1. Video presentation describing rationale (3-5 min.), 2. Audio guided meditation (8-10 min.), and 3. Other relevant in-app exercises (e.g., tips to help apply mindfulness to daily life). Each week a participant completes the PHQ-9 depression symptom survey within the app. While the parent U01 factorial trial is comparing 8 versions of LIFT that differ on 3 factors (NCT04038567), the LIFT COVID RCT will use the version of LIFT that includes no introduction call, app-based response to symptoms changes during the intervention period, and standard dose. The app-based approach to non-responders, defined as those whose PHQ-9 score has increased in comparison to the previous week or whose PHQ-9 score is  $\geq 20$ , uses the app's logic to display hovering messages and notifications within the app that may be applicable to the user. Depending on whether emotional or somatic depression symptoms are dominating the PHQ-9 score for the individual, a unique video is shown within the app that features the study interventionists leading a brief exercise in which the participant is coached by the interventionist in the application of mindfulness for the symptoms the participant has endorsed. The app-based approach to non-responders has 8 unique videos, 2 for each week (i.e., one tailored to emotional symptoms, one tailored to somatic symptoms).

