### ***Aim 3 procedures (cross-sectional focus groups)***

The goal of Aim 3 is to understand the barriers and facilitators to the successful use of the LIFT app from a patient's perspective within the context of a pandemic. We will use a stratified purposive design to sample 25 participants (~2 / mo.), a number sufficient for theme saturation, after 3 months post-discharge. The procedures will include a ~30-minute semi-structured one-on-one interview conducted by phone (based on participant preference and availability) by an experienced coordinator that will explore app access, use, and content. Theoretical sampling will ensure sufficient variability in characteristics that may influence experiences, stratifying cases by response to LIFT (high vs. low), LIFT use (high vs. low), demographics (age, gender), and baseline distress (moderate vs. high).

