If the patient is deemed not to be actively suicidal, they will be given contact information for the National Suicide Prevention Lifeline ([name]), a free, 24-hour hotline available to anyone in suicidal crisis or emotional distress. This will occur via the app for the intervention group and via email for control participants.

(7) As described in above, all concerns about participant safety will be discussed immediately with the PI including concerning, severe distress that does not involve suicidality. For these situations, once an “alert situation” is known, the PI will refer the participant if needed (based on a PI-led phone call) to local psychological resources as we have done previously with this well-tested Distress Management Protocol used successfully by [name] in 3 past clinical trials involving family members that used psychological distress outcomes. We will also make urgent and emergency referrals as needed based on information learned by any site PI on a site-by-site basis (see contact information above). It is important to note that this system has been developed in full partnership with the Duke IRB, who approve it in its entirety and have described it as a model for future patient safety in Duke-based clinical research. To date based on these studies that have included over 400 participants, we have found that <5% of participants will require a call from the PI during some point in the study period. Of those, none have required referral to acute psychiatric care after a detailed interview from the PI. After a disposition / solution has been made, both the resolution (and follow up) will be documented in the ‘contact log’ section of the data system for reporting to the DSMB.

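### The crisis-line contact goes out only through the app in the LIFT arm, so a participant who is not using the app could miss it

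*Combined protocol and SAP*

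**What the plan says.** The Suicidality Response Plan is item (6) of the participant oversight plans in Section 15. It applies to "any study participant who expresses suicidal thoughts in person, by telephone, or via the app at any point during the study". Its first listed trigger is a staff interaction, in person or by telephone; its second is automatic detection by the app system.

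After the three emergency situations, the plan turns to participants judged not to be actively suicidal. They are to receive the Lifeline contact, and the channel is stated: "This will occur via the app for the intervention group and via email for control participants".

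Other sections bear on whether a LIFT participant will be using the app:

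- Section 8 says of the automated message sent to the LIFT arm that "it will also provide a link to download the LIFT app platform and a unique ID code to activate it". The participant has to take both steps.
- Section 9 says that "the LIFT COVID RCT will use the version of LIFT that includes no introduction call".
- The Aim 3 procedures in Section 9 sample interviewees by high and low LIFT use.
- Section 7.b places the weekly in-app PHQ-9 within the 4-week intervention. Section 7.a puts follow-up on the telephone.

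**The concern.** The trigger for the plan does not depend on app use, but in the LIFT arm the stated delivery of the crisis-line contact may. A participant could raise suicidal thoughts on a follow-up call, be assessed as not actively suicidal, and have the contact placed only in an app that was never activated or is no longer opened. A control participant in the same position would be sent an email.

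What is at stake is patient safety, to a limited extent: a person who has just raised such a concern might not receive the number of a 24-hour line. No endpoint, analysis or clinical threshold is involved.

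**Working it through.** There is no plan figure to reproduce, so the check sets the sections side by side.

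**1. Is there another stated route for the Lifeline contact in the LIFT arm?** Sections 7 to 9 and all of the safety text in Section 15 were read for one. None is given. Several other safeguards carry no arm restriction:

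- an information sheet with mental health contact numbers, and a resource list at program start (oversight plans, item 4);
- staff assessment and referral to the PI (items 5 and 6);
- a call when the PHQ-9 suicidal ideation item is endorsed (Reporting Procedures);
- a PI mobile number reachable at all hours (adverse events paragraph).

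None of them is stated to include the Lifeline contact.

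**2. Can a concern arise when no app task is scheduled?** Section 3 puts the follow-up interviews at 2 and 5 months after randomization, and the program lasts about 1 month.

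- T2: 2 − 1 = about 1 month after the program ends.
- T3: 5 − 1 = about 4 months after the program ends.

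Both interviews include the PHQ-9 (Table 1). After randomization a LIFT participant has 4 weekly PHQ-9s in the app and 2 by telephone, 4 + 2 = 6 in all. Someone not using the app would complete only the 2 telephone ones. This count shows that a telephone trigger is a routine part of the schedule. It does not measure how many messages would be missed.

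**3. Is non-use of the app foreseeable?** Download and activation are left to the participant, there is no introduction call, and low use is a sampling stratum in Aim 3. This makes non-use plausible but gives no rate.

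**4. Does the wording necessarily mean display inside the app?** No. The documents use app, platform and app system loosely:

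- Section 8 has the platform notify participants of their group: "an automated SMS text message and/or email (per user preference) will be sent to the participant that alert them to their treatment group".
- Step 4 in the same section says that after T3 "traditional care control participants can access Lift if they wish via an email automatically sent from the LIFT platform".
- The response plan has the app system email or text staff.
- The Privacy paragraph has patients reach an app system through emailed or texted links.

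None of these says that the Lifeline contact travels that way.

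**5. Size.** The number affected would be the number of LIFT participants deemed not actively suicidal, times the proportion of them not using the app. The documents give neither quantity, so no headcount is offered.

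**The case against.** The strongest reply is that nearly the same people are already covered. The information sheet in item (4) is meant for passive suicidal ideation and for symptoms of depression, anxiety or PTSD, which is close to the group at issue, and it is not tied to an arm or to the app. Its content is not given, so the documents do not show that a LIFT non-user would lack crisis contacts. This stands as a limit on the size of the problem. It does not supply a stated route for the Lifeline contact.

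Second, the affected case already involves a live conversation. A participant flagged by the in-app PHQ-9 is using the app at that moment, so the channel fits. A non-user would come to notice through staff, who assess the situation and could simply give the number. That is likely in practice, and the call scripts are not in the documents. The protocol names a different channel, however, and does not ask staff to do this.

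Third, the wording may include SMS or email from the platform, in which case the gap disappears. That reading is open, and only the sponsor can settle it.

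Three smaller points also stand. Low use in a qualitative sampling frame is not the same as non-activation. Nothing says that app access ends at week 4. The control email has no stated fallback either, so a single channel is a weakness in both arms.

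**Conclusion.** The concern holds as a minor point. Under the rule as written, a LIFT participant who is not using the app could miss the Lifeline message. This rests on two assumptions: that delivery through the app means display inside it, and that staff do not give the number on the call. Neither can be confirmed or excluded from the documents.

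This is not a gap in suicidality coverage as a whole. One supplementary message may be missed by an unknown, probably small, number of people who will usually have just spoken with study staff.

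**What to change.** Amend the Lifeline sentence in the response plan so that:

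- the contact goes to participants in both arms by SMS or email, using the contact information entered for every participant at randomization (Section 8);
- staff read it out whenever the concern is handled on a call, including at T2 and T3;
- the in-app copy stays as an addition for the LIFT arm.

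Reading the number out also covers a control participant whose email goes unread. If the sponsor already intends platform SMS or email, the amendment only clarifies the wording.

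The cost is a sentence of protocol text, a line in the call script, and one message that staff may need to trigger after a telephone assessment. A crisis-line text could be seen by others on a shared phone, so the participant's stated contact preference should be followed; the control-arm email already carries a similar exposure. No threshold, clinical action or analysis changes.
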